## Protocol No: Version 2.17

## Date: 17 October 2022

## Abbreviations

3-point MACE	Major acute cardiovascular events (cardiovascular death, non-fatal myocardial infarction, non-fatal stroke)
ACR	Albumin/Creatinine Ratio
ADA	American Diabetes Association
AESI	Adverse events of Special Interest
ALAT	Alanine-Aminotransferase
ASAT	Aspartate-Aminotransferase
BASG	Bundesamt für Sicherheit im Gesundheitswesen
BMI	Body mass index
CHF	Congestive Heart Failure
CLTR	Department for Clinical Trials
CRF	Case Report Form
DKA	Diabetic Ketoacidosis
ECG	Electrocardiogram
eCRF	Electronic Case Report Form
eGFR	Estimated Glomerular Filtration Rate
EMEA	European Medicine Agency
EudraCT	European Union Drug Regulating Authorities Clinical Trials
FDA	Food and Drug Administration
FPFV	First Patient First Visit
GCP	Good Clinical Practice
GGT	Gamma-Glutamyl-Transferase
HDL	High Density Lipoprotein
IMI	Institute of Medical Informatics, Statistics and Documentation
ISF	Investigator Site File
INS	Institute Surveillance
KKS	Koordinierungszentrum für Klinische Studien
LBBB	Left bundle branch block
LDL	Low Density Lipoprotein
LPLV	Last Patient Last Visit

## Protocol No: Version 2.17

MCI	Myocardial Infarction
nt-proBNP	N-terminal pro b-type natriuretic peptide
NYHA	New York Heart Association
рН	Pondus Hydrogenii
RR	Riva Rocci Blood Pressure Measurement
SGLT-2	Sodium-dependent glucose cotransporter 2
SUSAR	Suspected Unexpected Serious Adverse Reaction
T2DM	Type 2 Diabetes Mellitus
TAPSE	Tricuspid Annular Plane Systolic Excursion
TMF	Trial Master File
TMG	Trial Management Group
TSC	Trial Steering Committee
UKPDS	United Kingdom Prospective Study
ULN	Upper Limit of Normal
UTI	Urinary Tract Infection
WMSI	Wall Motion Score Index

## Protocol No: Version 2.17

## Date: 17 October 2022

## **Synopsis**

Sponsor	Modical University of Graz				
Sponsor	Medical University of Graz  [name]				
	[name], Austria				
Principal Investigators	[name], Associate Professor				
	[name], MD, Associate Professor				
Indication	Patients with acute myocardial infarction				
Study design and phase	Randomized, prospective, placebo-controlled, double blind, multicenter				
	study in patients with acute myocardial infarction – a Phase III study.				
Study Short Title	Empagliflozin in acute myocardial infarction				
Keyword	SGLT-2 inhibition, acute myocardial infarction, heart failure				
Aims of the trial	Primary objective:				
	The primary objective is to investigate the impact of Empagliflozin on				
	biomarkers of heart failure in patients with myocardial infarction with and				
	without type 2 diabetes mellitus within 6 months after the event.				
	Secondary objective:				
	To investigate				
	- Short term changes of nt-proBNP levels				
	- Short term and intermediate term changes in echocardiography				
	parameters				
	- Change in levels of ketone body concentrations				
	- Change in HbA1c levels				
	- Change in body weight				
	- Number of hospital re-admissions due to heart failure or other causes				
	- Duration of hospital stay				
	- All-cause mortality				
Outcome measures of the trial	Primary outcome measures:				
	- Difference in the change of nt-proBNP levels between treatment				
	groups from randomization to week 26				
	Secondary outcomes measures:				
	Difference in the change of ejection fraction between treatment				
	groups from randomization to week 26				
	Difference in the change of ejection fraction between treatment				
	groups from randomization to week 6				

Protocol No: Version 2.17

	
 
Difference in the change of left ventricular diastolic function from randomization to week 26
 
				
	- Difference in the change of left ventricular diastolic function from				
	randomization to week 6				
	- Difference in the change of nt-proBNP levels between treatment				
	groups from randomization to week 6				
	- Difference in the change of HbA1c between treatment groups from				
	randomization to week 26 (in subjects with known T2DM)				
	
 
Difference in the change of body weight between treatment groups
 
				
	from randomization to week 6				
	- Difference in the change of body weight between treatment groups				
	from randomization to week 26				
	- Difference in the change of blood beta-hydroxybutyrate levels				
	between the treatment groups from randomization to week 6				
	- Difference in the change of blood beta-hydroxybutyrate levels				
	between the treatment groups from randomization to week 26				
	- Difference in the number of hospital re-admissions due to heart				
	failure between the treatment groups				
	- Difference in the number of hospital re-admissions for any cause				
	between the treatment groups				
	- Difference in the duration of hospital stay between the treatment				
	groups after initiation of the study treatment				
Number of patients	476 patients				
Time schedule	With reference to the trial:				
	EC Submission: NOV/2016				
	Local Authority Submission.: NOV/2016				
	First Patient In (FPFV): 11/MAY/2017				
	Last Patient In: 10/DEC/2021				
	Last Patient Out (LPLV): 03/MAY/2022				
	Data Base Lock: 17/MAY/2022				
	First Results available: JUL/2022				
	Clinical Study Report: SEP/2022				
	With reference to patients:				
	Duration of the treatment: 6 months				
Main inclusion criteria	1)Myocardial infarction with evidence of significant myocardial necrosis				
ivialii inclusion criteria	defined as a rise in creatinkinase >800 U/I and a troponin T- or I level >10x				
	ULN. In addition at least 1 of the following criteria must be met:				
	OLIV. III dudicion at least 1 of the following criteria must be met.				

Protocol No: Version 2.17

	- Symptoms of ischemia					
	- ECG changes indicative of new ischemia (new ST-T changes or new LBBB)					
	- Imaging evidence of new regional wall motion abnormality					
	2)18 – 80 years of age					
	3)Informed consent has to be given in written form.					
	4)eGFR > 45 ml/min/1.73m 					
	5)Blood pressure before first drug dosing: RR systolic >110mmHg					
	6) Blood pressure before first drug dosing: RR diastolic >70mmHg					
	7) First intake of study medication ≤72h after myocardial infarction after					
	performance of a coronary angiography					
Main exclusion criteria	1)Any other form of diabetes mellitus than type 2 diabetes mellitus, history					
	of diabetic ketoacidosis					
	2)Blood pH < 7,32					
	3)Known allergy to SGLT-2 inhibitors					
	4)Haemodynamic instability as defined by intravenous administration of					
	catecholamine, calciumsensitizers or phosphodiesterase inhibitors					
	5)>1 episode of severe hypoglycemia within the last 6 months under					
	treatment with insulin or sulfonylurea					
	6) Patients currently being treated with any SGLT-2 inhibitor (dapagliflozin,					
	canagliflozin, empagliflozin) or having received treatment with any SGLT-2					
	inhibitor within the 4 weeks prior to the screening visit					
Study medication	Active substance: Empagliflozin					
	Commercial name: Jardiance					
	Manufacturer: Boehringer Ingelheim					
Treatment plan	Empagliflozin, 10mg once daily orally administered or matched placebo					

Protocol No: Version 2.17

#### Date: 17 October 2022

#### 1. INTRODUCTION AND RATIONALE

Type 2 diabetes mellitus (T2DM) is associated with an about two to three-fold increased risk for cardiovascular events as compared to subjects without diabetes. The United Kingdom Prospective Study (UKPDS) was the first to demonstrate a reduction of macrovascular and microvascular complications in subjects with T2DM by an intensified glucose lowering treatment regimen with either insulin/sulfonylurea or metformin in the long term follow up. After Rosiglitazone was removed from the European market due to remaining uncertainty about the cardiovascular safety of this drug, the Federal Drug Administration (FDA) and the European Medicine Agency (EMEA) have issued new guidelines for new antihyperglycemic drugs to be licensed, requiring a thorough assessment of cardiovascular safety and in most cases the performance of a large cardiovascular outcome trial.

Sodium-dependent glucose cotransporter 2 (SGLT-2) is mainly expressed in human kidneys and small intestinal cells. In the proximal tubule of the nephron SGLT-2 is responsible for the reabsorption of approximately 90% of the filtrated glucose. Inhibition of SGLT-2 was shown to increase renal glucose excretion and to lower glucose. Subsequently, a number of SGLT-2 inhibitors were developed and are currently approved for the treatment of type 2 diabetes.

Recently, Zinman B. et al published the results of the EMPA-REG-OUTCOME trial where the cardiovascular impact of a glucose lowering regimen including Empagliflozin as compared to usual glucose control without an SGLT-2 inhibitor was investigated. The trial demonstrated an unexpected reduction in the primary composite endpoint, comprising cardiovascular death, non-fatal myocardial infarction and non-fatal stroke. The reduction was mainly driven by a 38% relative risk reduction in cardiovascular deaths; moreover they demonstrated an impressive 35% relative risk reduction in the secondary endpoint hospitalization for heart failure. Of note, the beneficial effects observed in the Empagliflozin group seem to occur very rapidly after commencing the treatment, as suggested by the early separation of the Kaplan-Meier curves. However, the mechanisms responsible for this finding remain unclear. Diuretic effects with subsequent impact on hemodynamics or potential cardioprotective effects of glucagon, which levels rise under the treatment with SGLT-2 inhibitors and the resulting rise in ketone bodies or a small increase in hematocrit have been suggested .

We hypothesize that Empagliflozin beneficially influences the increased pre- and afterload as well as it reduces the increased sodium reabsorption following myocardial damage with subsequent reduced cardiac output. Whether or not Empagliflozin has direct effects on myocardial remodelling has not been elucidated, yet. Moreover, recent animal data suggest that in failing heart ketone bodies seems to be increasingly important as energy source. Empagliflozin has been shown to increase levels of ketone bodies, which might has a beneficial impact on the metabolism and energy supply of the failing heart.

In addition, although SGLT-2 is not expressed in human myocardium, direct, non-SGLT-2 mediated effects on the heart muscle cannot be excluded, given that the molecule is small in size.

[figure not shown]

Figure 1 Summary of potential beneficial mechanisms of Empagliflozin used after MCI

The aim of this mechanistic study is to investigate the impact of Empagliflozin on cardiac function and biomarkers for heart failure in patients with acute myocardial infarction. Since previous trials in acute myocardial infarction using aldosterone blockers demonstrated that an early intervention might be crucial for a beneficial outcome, we have chosen to start treatment within 72 hours after performance of a coronary angiography for acute myocardial infarction.

## 1.1 Aim of the study

The aim of this mechanistic study is to investigate the impact of Empagliflozin on cardiac function and biomarkers of heart failure in patients with acute myocardial infarction.

#### 1.2 Study hypothesis

Treatment with the SGLT-2 inhibitor Empagliflozin, commenced early after acute myocardial infarction will reduce the biomarker for heart failure nt-proBNP more effectively than placebo within 6 months after the event.

## 2. OBJECTIVES AND OUTCOMES

## 2.1 Primary objective

The primary objective is to investigate the impact of Empagliflozin on biomarkers of heart failure in patients with myocardial infarction with and without type 2 diabetes mellitus within 6 months after the event.

Protocol No: Version 2.17

#### Date: 17 October 2022

## 2.2 Secondary objectives

#### To investigate

- Short term changes of nt-proBNP levels
- Short term and intermediate term changes in echocardiography parameters
- Change in levels of ketone body concentrations
- Change in HbA1c levels
- Change in body weight
- Number of hospital re-admissions due to heart failure or other causes
- Duration of hospital stay
- All-cause mortality

#### 2.3 Safety objectives

- All-cause mortality
- Number of serious adverse events
- Number of hypoglycemic events
- Number of genital infections
- Number of ketoacidotic events
- Changes in liver function parameters (AST, ALT, GGT)
- Changes in renal function parameters (creatinine, eGFR)

## 2.4 Primary outcomes

Difference in the change of nt-proBNP levels between treatment groups from randomization to week 26

## 2.5 Secondary outcomes

- Difference in the change of ejection fraction between treatment groups from randomization to week 26
- Difference in the change of ejection fraction between treatment groups from randomization to week 6
- Difference in the change of left ventricular diastolic function from randomization to week 26
- Difference in the change of left ventricular diastolic function from randomization to week 6
- Difference in the change of nt-proBNP levels between treatment groups from randomization to week 6
- Difference in the change of HbA1c between treatment groups from randomization to week 26 (in subjects with known diabetes mellitus Type 2)
- Difference in the change of body weight between treatment groups from randomization to week 6
- Difference in the change of body weight between treatment groups from randomization to week 26
- Difference in the change of blood beta-hydroxybutyrate levels between the treatment groups from randomization to week 6
- Difference in the change of blood beta-hydroxybutyrate levels between the treatment groups from randomization to week 26
- Difference in the number of hospital re-admissions due to heart failure between the treatment groups
- Difference in the number of hospital re-admissions for any cause between the treatment groups

Protocol No: Version 2.17 Date: 17 October 2022

- Difference in the duration of hospital stay between the treatment groups after initiation of the study treatment

#### 3. STUDY DESCRIPTION

#### 3.1 Design

This is a randomized, double-blind (patients and physicians), placebo controlled multi-center study to evaluate the effect of Empagliflozin 10mg once daily (p.o.) for 26 weeks on cardiac function and biomarkers for heart failure in patients with acute myocardial infarction (Figure 1). The study will be conducted in 11 sites in Austria (Appendix B) with an aim to enrol 476 patients (Figure 2) to evaluate the overall study hypothesis.

[figure not shown]

Figure 2 Study Flow Chart

## 3.2 Duration of study

It is anticipated that the study will run for 30 months.

#### 4. STUDY POPULATION

We will study subjects after an acute myocardial infarction. We aim to recruit 150 subjects with established diabetes mellitus type 2.

#### 4.1 Inclusion criteria

- 1) Myocardial infarction with evidence of significant myocardial necrosis defined as a rise in creatinkinase >800 U/I and a troponin T-level (or troponin I-level) >10x ULN. In addition at least 1 of the following criteria must be the met:
  - Symptoms of ischemia
  - ECG changes indicative of new ischemia (new ST-T changes or new LBBB)
  - Imaging evidence of new regional wall motion abnormality
- 2) 18 80 years of age

#### Protocol No: Version 2.17

#### Date: 17 October 2022

- 3) Informed consent has to be given in written form
- 4)  $eGFR > 45 ml/min/1.73 m^2$
- 5) Blood pressure before first drug dosing: RRsystolic>110mmHg
- 6) Blood pressure before first drug dosing: RRdiastolic>70mmHg
- 7) First intake of study medication ≤72h after myocardial infarction after performance of a coronary angiography

#### 4.2 Exclusion criteria

- 1) Any other form of diabetes mellitus than type 2 diabetes mellitus, history of diabetic ketoacidosis
- 2) Blood pH < 7,32
- 3) Known allergy to SGLT-2 inhibitors
- 4) Haemodynamic instability as defined by intravenous administration of catecholamine, calciumsensitizers or phosphodiesterase inhibitors
- 5) >1 episode of severe hypoglycaemia within the last 6 months under treatment with insulin or sulfonylurea
- 6) Females of child bearing potential without adequate contraceptive methods (i.e. sterilisation, intrauterine device, vasectomised partner; or medical history of hysterectomy)
- 7) Acute symptomatic urinary tract infection (UTI) or genital infection
- 8) Patients currently being treated with any SGLT-2 inhibitor (dapagliflozin, canagliflozin, empagliflozin) or having received treatment with any SGLT-2 inhibitor within the 4 weeks prior to the screening visit

#### 4.3 Withdrawal criteria

Subjects may be withdrawn from the study at the discretion of the Investigator or Sponsor due to a safety concern or if judged non-compliant with trial procedures. A subject must be withdrawn from treatment of the following applies:

- Subject chooses to withdraw from the study at any time
- Adverse event requires unblinding of the study medication
- Pregnancy or intention of becoming pregnant
- Intolerable adverse effects
- Major violation of the study protocol
- Occurrence of an exclusion criterion
- Other circumstances that would endanger the health of the subject if he/she were to continue his/her participation in the trial.

Reasons for withdrawals and discontinuation of any subject from the protocol have to be recorded.

Protocol No: Version 2.17

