## 4.6. Tracking of drop out patients

In order to guarantee a 100% follow-up of the mortality in this study, we would like to apply to be able to call up the mortality data of the study participants from Statistics Austria for the period of study participation. This can increase the quality of the data even further and thus improves the significance of the study.

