#### 7.2 Data analysis

Patient characteristics will be summarized. Summaries of continuous variables will be presented as means and standard deviations, if normally distributed, and as medians and inter-quartile ranges for skewed data, whilst categorical variables will be presented as frequencies and percentages. The analysis will be performed according to the intention to treat principle. All statistical tests will be two-tailed with a 5% significance level.

Analysis will be based on the intention to treat cohort, while a sensitivity analysis for the per-protocol group will be done in addition. A detailed statistical analysis plan including pre-specified subgroup analyses will be finalized ahead of database lock.

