5.2 Analysis Populations

5.2.1 Intention to Treat Population (ITT)

The ITT population includes all patients who were randomized and received at least one dose of the study medication (i.e. Empagliflozin or Placebo). The ITT population will be used for the primary efficacy analysis.

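### Protocol 4.3 lets patients be taken out of the study for non-compliance, and nothing keeps the week-26 NT-proBNP sample that the intention-to-treat analysis needs

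*Protocol*

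**What the plan says.** Protocol 4.3 contains two rules. The first is discretionary and concerns leaving the study: "Subjects may be withdrawn from the study at the discretion of the Investigator or Sponsor". Two grounds are given for this, namely safety and failure to comply with the procedures of the trial. The second is mandatory and concerns study drug: "A subject must be withdrawn from treatment of the following applies". The list under the second rule blurs the distinction, because it includes the patient's own decision to leave the study and circumstances that make continued participation in the trial unsafe. Reasons for withdrawal and discontinuation must be recorded.

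Follow-up of patients who drop out is covered in Protocol 4.6 and 4.7. Its stated purpose is "In order to guarantee a 100% follow-up of the mortality in this study", through a query to the national statistics office. Neither section mentions NT-proBNP or Visit 4.

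On analysis, Protocol 7.2 states: "Analysis will be based on the intention to treat cohort, while a sensitivity analysis for the per-protocol group will be done in addition". SAP 5.2.1 does not make compliance a condition: "The ITT population includes all patients who were randomized and received at least one dose of the study medication". SAP 7.1 analyses NT-proBNP with a linear mixed model, takes the treatment contrast at week 26, imputes nothing and assumes MAR. SAP 5.4 and 7.2.1 give the missing-data sensitivity analysis: multiple imputation by chained equations with ten data sets. Poor drug intake enters only through the per-protocol set in SAP 5.2.2.

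**The concern.** An intention-to-treat estimate needs the week-26 value of each patient in the set, whether or not the drug was taken. A rule that ends study participation for non-compliance works against this. It acts after randomisation, and non-compliance may be related to tolerability, and so to arm, or to how the patient's heart is recovering. If so, the missing week-26 values differ from what the mixed model predicts from observed data, and the MAR assumption fails.

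The planned analyses would not show this. Multiple imputation as described draws on the same assumption. Secondary efficacy analyses III and IV regress week-26 change without imputation. A patient removed before Visit 2 has only a baseline value, which enters the model as a covariate, so that patient adds no post-baseline information. The 10% dropout allowance protects power; it does nothing about bias.

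The rule also has no analytic purpose, since the per-protocol set already deals with patients who took too little medication.

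**Working it through.** **The plan's own figures first.** Inputs from Protocol Appendix A: means 653.66 (baseline) and 282.66 (6 months); SDs 772.98 and 289.60; correlation 0.85; relative reduction 0.40; two-sided 5% alpha; 80% power.

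- Planned difference: 0.40 × (653.66 − 282.66) = 148.4.
- Variance ratio: 289.60² / 772.98² = 0.1404.
- SD of change: 772.98 × √(1 + 0.1404 − 2 × 0.85 × √0.1404) = 548.5.
- Sample size: 2 × (1.960 + 0.842)² × 548.5² / 148.4² = 214.4, so 215 per arm against 216 stated. This reproduces within one patient.
- Dropout: 216 × 1.10 = 237.6, so 238 as stated. A 10% loss leaves 238 × 0.90 = 214 per arm, with 80.0% power on this change-score SD.

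**Shift in the estimate.** The documents give no rate of discretionary withdrawal and no size of departure. Assumptions: a share w of each arm lacks a week-26 value; missing active-arm patients differ from their MAR prediction by 0.5 SD; missing placebo patients do not differ.

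Shift = w × 0.5 SD; standard error = √(2/n) SD, with n = 238 × (1 − w).

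| w | n per arm | Shift (SD) | SE (SD) | Shift / SE |
|---|---|---|---|---|
| 5% | 226 | 0.025 | 0.0941 | 0.27 |
| 10% | 214 | 0.050 | 0.0967 | 0.52 |

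**Set against the planned difference, at w = 10%.** The answer depends on which SD is meant.

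- Baseline-adjusted SD, closer to the SAP model: 289.6 × √(1 − 0.85²) = 153. Shift 0.05 × 153 = 7.6; 7.6 / 148.4 = 5%.
- Change-score SD, as in Appendix A: 0.05 × 548.5 = 27; 27 / 148.4 = 18%.
- If both arms depart equally, the shifts cancel and the result is zero.

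These figures are on the raw scale of Appendix A. SAP 5.3.1 allows a log transformation, which would change them.

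**The case against.** Several points on the other side stand.

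- **The rule is permissive.** It says that subjects may be withdrawn. A reader might infer that it deletes week-26 outcomes as a matter of course, but the documents do not say how often it was used. NT-proBNP values collected before withdrawal (baseline, and weeks 6 and 12 where reached) stay in the mixed model.
- **The listed events are a different rule.** A reader might infer that intolerable adverse effects and the other listed events also end follow-up. The text requires only withdrawal from treatment for these and does not say that visits stop. Retention is unstated, which is a drafting gap, not a rule that removes these patients.
- **Some deviators appear to have been kept.** SAP 5.2.2 lists patients with under 75% of medication separately from those without a week-26 evaluation, and refers to ineligible patients who stayed in the trial.
- **Not all the data are recoverable.** The trigger is non-compliance with trial procedures, not only with medication. Someone who does not attend visits may give no week-26 sample under any wording.
- **The 10% is not all due to this rule.** The dropout allowance is not divided by cause. It would also cover withdrawal of consent and loss to follow-up, which the wording change cannot prevent.
- **Timing.** Protocol version 2.17 is dated 17 October 2022, after the last patient out (3 May 2022) and the database lock (17 May 2022) given in the synopsis. Rewording 4.3 at this version cannot recover past samples.

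These points limit the size and the remedy. They do not remove the concern: non-compliance is an express ground for leaving the study, no passage restores the week-26 sample, and no planned analysis relaxes MAR.

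**Conclusion.** The point holds as a weakness that should be put right. Protocol 4.3 permits removal from the study for non-compliance, does not cleanly separate this from stopping treatment, and is not balanced by any provision for week-26 sampling. With a primary analysis and a missing-data check that both assume MAR, the rule can produce informative missing values that would go undetected.

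The size is illustrative: 0.27-0.52 standard errors for 5-10% missing, with an assumed 0.5 SD departure in the active arm only. The upper figure assigns the whole dropout allowance to informative loss. At 10% the shift is about 5% of the planned difference on the baseline-adjusted SD and about 18% on the change-score SD. The direction is not known. It would be wrong to read these figures as an estimate of actual bias in this trial.

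**What to change.** **Protocol 4.3**

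- Remove non-compliance as a ground for leaving the study.
- Reconcile the passages on withdrawal from the study and withdrawal from treatment, so that each listed event clearly belongs to one or the other.
- State that patients who stop study medication remain in follow-up, with the already scheduled week-26 NT-proBNP sample, where they consent.
- Leave the safety-concern ground and all treatment-stopping criteria as they are.

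**SAP**

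- Report study withdrawals by arm and reason; Protocol 4.3 already requires the reasons to be recorded.
- Add a delta-adjusted or reference-based MNAR sensitivity analysis of the primary endpoint. A delta-adjusted version should cover a range of departures, applied to the active arm alone and to both arms.

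The SAP changes remain usable where visits are already past; the protocol wording helps only visits still to come. The cost is a few sentences of text, some visits by patients who are off drug, and a little more analysis work. Visit 4 is already in the schedule.

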## 5. VISIT PROCEDURES, MEASUREMENTS AND ASSESSMENTS

#### 5.1 Recruitment and screening

Sites will recruit competitively and sites will receive compensation for their work based on a per-patient fee. The clinic staff of the intensive care unit informs patients about the possibility of being enrolled in this study. No study-related procedures are undertaken before obtaining informed consent. The study team in detail explains the study procedures and asks the participant about their willingness to participate in this research study. After informed consent is signed and obtained, participants are given a signed copy of the informed consent document and are assigned a screening identification number.

After obtaining informed consent at the screening visit, subject's eligibility will be further assessed and documented by using a source data form with a list of inclusion and exclusion criteria, medical history (including all medications past and current) will be acquired and the following measurements will be performed: body weight, height, blood pressure, ECG and blood parameters (see Table 2). Laboratory results up to 2 days before screening can be used to test eligibility for the trial.

Subjects unable to provide written informed consent will not be included in the study.

Protocol No: Version 2.17

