## 5.4 Visit procedures

#### Visit 1 - Screening/Enrolment Visit (Day 0 - hospital stay)

- Obtain informed consent of potential participant verified by signature on study informed consent form (10.5)
- Collect blood to check inclusion criteria (creatinkinase, troponin T (or troponin I), eGFR, blood pH, nt-proBNP) (5.5.7)
- Collect and prepare blood samples for biobank (5.5.6)
- Perform echocardiography (5.5.7)
- Obtain demographic information, medical history, medication history, alcohol and tobacco use history (5.5.1)
- Record vital signs (5.5.3)
- Measure body weight and body height (5.5.4)
- Verify inclusion/exclusion criteria (4.2 and 4.3)
- Randomize the subject (5.2)
- Dispense the study medication for trial period (9.4)
- Adjust concomitant antihyperglycemic medication
- Assessment of side effects and patient safety before discharge (5.5.8)

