#### Protocol No: Version 2.17

#### Date: 17 October 2022

Fasting glucose	Х	Х	Х	Х
Myoglobin	X			
pH (arterial/venous)	Х			
Urine Albumin/Creatinine Ratio (ACR)	Х	Х		Х

Table 2 Summary of blood tests at each study visit

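### The supplied plan schedules no pregnancy test before the first dose and does not name pregnancy as an exclusion, although Protocol 4.3 stops treatment for pregnancy: a rare, cheaply closed safety gap

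*Protocol*

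**What the plan says.** **Stop rule.** Protocol 4.3 lists circumstances in which a patient must come off treatment. One is "Pregnancy or intention of becoming pregnant". It stands apart from the entry for a newly occurring exclusion criterion.

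**Entry rule.** Protocol 4.2, criterion 6, repeated in SAP 3.2.2, excludes "Females of child bearing potential without adequate contraceptive methods (i.e. sterilisation, intrauterine device, vasectomised partner; or medical history of hysterectomy". None of the eight exclusions is pregnancy itself. The age range in 4.1 starts at 18.

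**Visit 1 checks.** Protocol 5.4 has the site "Collect blood to check inclusion criteria (creatinkinase, troponin T (or troponin I), eGFR, blood pH, nt-proBNP) (5.5.7" and, before randomisation, "Verify inclusion/exclusion criteria (4.2 and 4.3". Protocol 5.1 adds that "Laboratory results up to 2 days before screening can be used to test eligibility for the trial".

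**Supply.** Protocol 9.1 has the medication packed as 26-week supplies, and Table 1 marks dispensing once, at Visit 1.

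**Other mentions of pregnancy.** Protocol 11.1 names pregnancy forms as source data, and SAP 8.2 provides for describing the outcome of any recorded pregnancy. Both concern recording a pregnancy, not looking for one.

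**The concern.** The plan treats pregnancy as a reason to stop the drug, yet in the supplied text it has no scheduled means of knowing whether that reason already applies when the first tablet is taken. Asking about contraception is a proxy: it identifies women at low risk of pregnancy, not women who are not pregnant. Two of the situations that criterion 6 accepts, an intrauterine device and a vasectomised partner, leave a woman able to conceive.

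At stake is participant safety in a very small group: exposure that the plan itself would end if the pregnancy were known. With the whole supply handed over at Visit 1 and no pregnancy test scheduled at later visits, discovery after entry would depend on self-report or chance.

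**Working it through.** The plan gives no figure on this point, so there is none to reproduce. The check is a reading of every place where an entry test would appear, followed by a rough size under stated assumptions.

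**Step 1: where a test could be scheduled**

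| Place | What it contains | Pregnancy test? |
|---|---|---|
| Protocol 5.1, screening measurements | weight, height, blood pressure, ECG, Table 2 bloods | no |
| Protocol Table 1, and its copy in SAP 3.4 | all scheduled procedures by visit | no row |
| Protocol 5.4, Visit 1 eligibility bloods | creatine kinase, troponin, eGFR, pH, NT-proBNP | no |
| Protocol Table 2 | full laboratory list; the only urine test is the albumin/creatinine ratio | no row |

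Table 2 has one row of marks without a label in the supplied copy. It lies next to the sodium/potassium/chloride row, which has a label and no marks, so it is a broken table row and not a lost test.

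**Step 2: follow one patient through the text**

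Take a woman of child-bearing potential with an intrauterine device who is pregnant and does not know it.

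- Criterion 6 does not exclude her, because her method is on the accepted list.
- No other exclusion in 4.2 refers to pregnancy.
- The Visit 1 check of 4.2 and 4.3, read literally, brings in the 4.3 list. That catches a pregnancy she reports, not one she is unaware of.
- No laboratory result would reveal it.
- She is randomised and receives the supply.

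**Step 3: size**

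Inputs:
- N = 476 (Protocol 3.1).
- p = share of patients who are women of child-bearing potential passing criterion 6. Not in the documents; assumed 1% to 5%.
- q = share of those women with an unrecognised pregnancy at entry. Not in the documents; assumed 0.1% to 1%.

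Expected cases E = N × p × q.

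- Low: 476 × 0.01 = 4.76 women; 4.76 × 0.001 = 0.0048 cases.
- High: 476 × 0.05 = 23.8 women; 23.8 × 0.01 = 0.238 cases.
- On empagliflozin (238 of 476, one half): 0.0024 to 0.119 cases.

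Rate needed to expect one case, q = 1 / (N × p):

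- with 23.8 women: 1 / 23.8 = 4.2%;
- with 4.76 women: 1 / 4.76 = 21.0%.

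**Step 4: effect on the analysis**

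Protocol 4.3 requires withdrawal from treatment, and the ITT population in SAP 5.2.1 keeps everyone randomised and dosed. A single case would be 1/476 = 0.2% of the sample. Neither the sample size nor the primary model depends on it.

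**The case against.** The case against making the point is substantial.

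- **No contradiction.** A rule that stops treatment for a known event does not oblige the plan to screen for an unknown one. This stands. The documents are not inconsistent here; a step is absent.
- **Mostly handled already.** Two of the four situations accepted by criterion 6, sterilisation and hysterectomy, leave practically no chance of pregnancy. Visit 1 also includes a history and an examination. This stands, and it is why the gap is confined to unrecognised pregnancy in a small subset.
- **Rare, and harm not documented.** The rates above are assumptions, and even the highest gives about a quarter of one case. The benefit-risk text in Protocol 5.6 describes no fetal hazard. Both stand; the argument rests on the plan's own stop rule and on low cost.
- **Too late for this trial.** The Synopsis gives "Last Patient In: 10/DEC/2021", which is 311 days before version 2.17 of 17 October 2022. This stands: no enrolment can be altered. It does not make the written entry procedure complete for a reader who reuses it.
- **A test may be described elsewhere.** Protocol 5.1 refers to a "source data form with a list of inclusion and exclusion criteria", 11.1 to pregnancy forms and 11.6 to procedure manuals. None was supplied, and consent pages were removed. This limits certainty, although the schedule and laboratory tables, where a protocol test would normally appear, are present.

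A reader might infer that the protocol admits women known to be pregnant. The documents do not support that. Read literally, the Visit 1 check includes the 4.3 list. If that reference is a slip for 4.1 and 4.2, 4.3 would still require a known pregnancy to come off treatment.

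**Conclusion.** The point holds in a limited form. In the supplied text, pregnancy is a mandatory stop but neither a named exclusion nor something tested for before dosing, so an unrecognised pregnancy in a woman with an accepted contraceptive method would pass every listed criterion. Under the assumed rates the trial expects between 0.005 and 0.24 such cases, 0.002 to 0.12 on active drug. There is no consequence for sample size or primary analysis. It is a cheap improvement that the sponsor could make, not a flaw in the trial's conclusions.

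Two stronger conclusions should not be drawn. The documents do not show that pregnant women were dosed or that sites did no testing; routine care or the unsupplied forms may have covered it. Nor do they establish what harm a case would bring.

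**What to change.** For the plan as designed, or any reuse of it:

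1. Name pregnancy as an exclusion in Protocol 4.2.
2. Add serum hCG for women of child-bearing potential to the Visit 1 eligibility blood draw and to Tables 1 and 2, with the result required before the first dose. Accept results from up to 2 days before screening, as 5.1 already does for other laboratory values.

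Serum is the safer choice. Table 2 does list "Urine Albumin/Creatinine Ratio (ACR" at Visit 1, but the Visit 1 procedures mention no urine collection, so urine is not shown to be in hand before dosing.

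The cost is one extra laboratory parameter at one visit in a small subset, from blood already drawn, and one line in 4.2. The small downside is that the result must arrive inside the 72-hour dosing window of inclusion criterion 7.

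For the enrolled cohort, one sentence in the report should say whether pregnancy testing was done at entry. SAP 3.2.2 should stay as it is, because it records the criteria used and per-protocol exclusion (a) in SAP 5.2.2 depends on them.

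Separately, and only as a clerical matter, the Visit 1 reference to 4.2 and 4.3 probably should read 4.1 and 4.2. The same list sends the eligibility blood draw to 5.5.7, which is echocardiography.
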